 Yes  No	Use the Center for Magnetic Resonance Research (CMRR) as a study location?	
Complete the CMRR pre-IRB ancillary review
 
Contact: [contact]
	prior to IRB approval; These groups each have their own application process.
 Yes  No	Include the use of recombinant or synthetic nucleic acids, toxins, or infectious agents?	STOP – Complete the Medical Template Protocol (HRP-590)	
 Yes  No	Include the use of human fetal tissue, human embryos, or embryonic stem cells?	STOP – Complete the Medical Template Protocol (HRP-590)	
 Yes  No	Include PHI or are you requesting a HIPAA waiver?	
If yes, HIPCO will conduct a review of this protocol.
 
Contact: [contact]
	
 Yes  No	
Use data from CTSI Best Practices Integrated Informatics Core (BPIC)
 
Formerly the AHC Information Exchange (AHC-IE)?
	
The Information Exchange ancillary review will be assigned to your study by IRB staff
 
Contact: [contact]
	Approval must be received prior to IRB approval.
 Yes  No	Use the Biorepository and Laboratory Services to collect tissue for research?	
STOP – Complete the Medical Template Protocol (HRP-590)
 
The BLS ancillary review will be assigned to your study by IRB staff.
 
Contact: [name] [contact]
	
 Yes  No	Have a PI or study team member with a conflict of interest?	
The Col ancillary review will be assigned to your study by IRB staff
 
Contact: [contact]
	
 Yes  No	Need to be registered on clinicaltrials.gov?	
If you select "No" in ETHOS, the clinicaltrials.gov ancillary review will be assigned to your study by IRB staff
 
Contact: [contact]
	
 Yes  No	Require registration in OnCore?	
If you select "No" or "I Don't Know" in ETHOS, the OnCore ancillary review will be assigned to your study by IRB staff
 
Contact: [contact]
	Does not affect IRB approval.

PROTOCOL COVER PAGE

RCT: Randomized controlled trial

PI: Principal Investigator

NIH: National Institutes of Health

AA: Alzheimer's Association

SLUMS: St. Louis University Mental Status

MBA: Minnesota Board on Aging

CAB: Community Advisory Board

PWML: Person with Memory Loss

LAR: Legally authorized representative

DNT: Director of Nursing and Technology

RC: Research Coordinator

ICER: Incremental cost-effectiveness ratio

ISM: Independent study monitor

DSM: Data & Safety Monitoring

1.0 Objectives

Purpose: Sensor-based technologies that operate remotely and are non-invasive could assist family caregivers monitor the daily function of persons with Alzheimer's disease or a related dementia (ADRD). The eNeighbor technology platform includes a combination of remote sensors that are located in key areas of a person with ADRD's home (e.g., bed, medicine cabinet or refrigerator doors, toilet, living rooms). Such sensors can immediately communicate any function that is outside of an expected threshold for the person with ADRD to both a family caregiver and a care professional (e.g., nurse care manager). The goal of the remote health monitoring technology such as eNeighbor is to prevent negative health transitions such as falls or wandering events, and thus provides a more proactive intervention model than many clinical protocols that are currently delivered to family caregivers of persons with ADRD. The Lutheran Home Association, a non-profit long-term care provider located in Belle Plaine, Minnesota, has deployed eNeighbor in residential and home settings the past 5 years.

The objective of this 5-year demonstration project is to build on the work of The Lutheran Home Association and conduct an embedded experimental mixed methods evaluation to determine the efficacy of the eNeighbor technology in improving outcomes among persons with ADRD living in the community and their family caregivers.

In collaboration with a 15-member Community Advisory Board that includes community care providers, healthcare organizations, and ADRD caregivers themselves, the proposed 5-year project will build on the current efforts of TLHA to evaluate eNeighbor remote monitoring technology for persons with ADRD living in the community and their family caregivers. We anticipate that the successful completion of the project aims will position the eNeighbor as an innovative, stakeholder-centric service that offers robust support for family caregivers of persons with ADRD in the community.

The Specific Aims are as follows:

1) To determine the efficacy of remote sensor technology over an 18-month period for 100 persons with ADRD and their caregivers randomly assigned to an eNeighbor treatment condition when compared to 100 usual care controls. We hypothesize:

Hx. 1) Significant ($p < .05$) improvements in caregiver self-efficacy and sense of competence in managing a relative's ADRD;

Hx. 2) Significant reductions in caregiver distress (e.g., subjective stress, or feelings of emotional fatigue and role entrapment; depressive symptoms);

Hx. 3) Significant delay of or reductions in health transitions (falls, wandering) and service utilization (hospitalizations, nursing home admission) for persons with ADRD; and

Hx. 4) Greater cost-effectiveness associated with a person with ADRD's health service use.

2) To "embed" evaluation components: a) during the randomized controlled evaluation through the administration of open-ended survey items to all ADRD caregivers in the eNeighbor treatment condition every 6 months to examine the utility of the remote health monitoring technology; and b) at the conclusion of the 18-month evaluation by purposively sampling 15

PROTOCOL TITLE: A Proactive Health Monitoring Intervention for Dementia Caregivers: The eNeighbor

ADRD caregivers who reported positive acceptance on the embedded qualitative and quantitative 6-, 12-, and 18-month system reviews and 15 ADRD caregivers who reported low acceptance on the embedded qualitative and quantitative 6-, 12-, and 18-month system reviews to participate in semi-structured interviews. The interviews will help the research team determine why the health monitoring intervention was or was not efficacious; and

3) To engage stakeholders on a quarterly basis throughout the 5-year project with the goal of enhancing the utility (via community-based participatory approaches)⁶⁷ and stakeholder-relevance of eNeighbor implementation and evaluation for family caregivers of persons with ADRD.

2.0 Background

2.1 Significance of Research Question/Purpose:

Alzheimer's disease or a related dementia (ADRD) is extremely challenging to manage and treat due to complexities in detection, interacting symptoms, and length of progression.¹ Because persons with dementia rely heavily on informal (i.e., unpaid) sources of care, the prevalence of Alzheimer's disease (AD) has a staggering effect on families. In 2013, 80% of the 5.2 million persons with AD in the United States (U.S.) were cared for by a family member and 15.4 million individuals provided unpaid care to a person with ADRD.¹ There is no one consistent definition of *caregiving*, but in its most global sense caregiving refers to attending to an individual's health needs. More specific definitions emphasize that caregiving includes provision of assistance with one or more activities of daily living (such as bathing, dressing, transferring).^{2,3} In the dementia context, caregiving can extend to the management of symptoms such as memory loss, behavioral disruptions, and similar concerns. The typical AD caregiver in the U.S. is female, 48 years of age (suggesting multiple role responsibilities in addition to family care) and assists a relative who is 78 years old.⁴ A well-established literature demonstrates the adverse effects of ADRD care on family members including impaired physical health and immune system response,⁵⁻⁷ financial strain,⁴ degradation in social well-being, and increased prevalence of depression, anxiety, or other negative mental health symptoms.^{8,9} With the accumulation of evidence demonstrating the physical, financial, social, and psychological risks of dementia family care, a series of clinical interventions have been developed and evaluated. Meta-analyses and systematic reviews suggest moderate overall benefits of these interventions for ADRD caregivers and their care recipients.^{1,5,10-12}

Although family members of persons with dementia are willing to utilize technology to improve their respective caregiving situations, few studies have determined whether various technologies can help families alleviate negative outcomes for caregivers of persons with ADRD.¹³⁻²⁰ Among the potential benefits of technological interventions is the ability to assist family caregivers of persons with ADRD regardless of geographical distance, which is in contrast to standard ADRD caregiver interventions where treatment is often delivered face-to-face to family caregivers in

PROTOCOL TITLE: A Proactive Health Monitoring Intervention for Dementia Caregivers: The eNeighbor

need. Technology-based interventions also have the potential to overcome another barrier to ADRD caregiver interventions: that of time and scheduling.²¹ Family members can often utilize and benefit from various types of technology-based interventions at any time, thus making these approaches asynchronous. Technology interventions evaluated include telephone-based approaches (conference calls among family members of persons with ADRD, automated telephone messages and support, respite calls for persons with ADRD) and computer or internet-based strategies (e.g., DVD-based delivery of education and support, online discussion boards, electronic reminders, computer-based encyclopedias and information resources, online decision-making support).²² While technology interventions for ADRD caregivers have shown some promise, small samples, inconsistent measurement, and lack of high quality randomized controlled evaluations suggest the need for further research.^{15,23-36}

The proposed demonstration project will advance scientific knowledge, technical capability, and clinical practice as they pertain to ADRD caregiver interventions. Although research on family caregiving has served as a platform for multidisciplinary research,^{37,38} a critical gap in this literature is the lack of randomized controlled studies that evaluate advanced, low-cost, high potential technologies to alleviate the stressors and other negative outcomes associated with everyday ADRD care. The proposed project will be one of very few clinical trials that evaluate the efficacy of home-based sensor technologies on actual user outcomes (e.g., family caregivers, older adults) in a real world environment using an experimental design.^{19,22} Specifically, Healthsense, Inc. has developed a suite of remote monitoring tools called the eNeighbor, and the Lutheran Home Association (TLHA: a non-profit, long-term care provider) has been implementing eNeighbor in residential care settings and home environments in Minnesota and Wisconsin as part of its routine services offered over the past 5 years. The overarching objective of eNeighbor is to lower the cost of care, increase independence of disabled older persons, and enhance quality of life for chronically disabled older persons and their family caregivers by allowing older persons to remain in their homes safely for as long as possible.

2.2 Preliminary Data:

A number of case studies and survey research efforts establish the feasibility of the eNeighbor remote sensor technology in various residential and community-based long-term care settings and its potential to prevent falls, medical emergencies, and similar negative health events.⁶⁵ An oft-repeated sentiment of users and family caregivers is that the technology represents a “godsend”⁶⁶ with no adverse events reported. The feasibility of eNeighbor has been further established with dementia caregivers in home settings through peer-reviewed pilot research by the study consultant, [name] (who has expertise in studying health technology for ADRD caregivers as PI; R21 AG029224).¹⁴⁻¹⁶ Using a controlled design, Kinney and colleagues¹⁴ enrolled 28 individuals who were caring for a co-resident family member with dementia (13 spouses, 15 adult children). When compared to baseline, intervention group caregivers ranked meaningful activity and enjoyment as significantly more important than usual care controls at follow-up. Qualitative interviews were used to supplement and elaborate upon the quantitative findings; specifically, several caregivers reported adaptation to the constant presence of the

PROTOCOL TITLE: A Proactive Health Monitoring Intervention for Dementia Caregivers: The eNeighbor

eNeighbor technology in the weeks immediately following installation. As one caregiver stated, "For the first few weeks I thought about it every time I opened something. I thought about it being recorded, but now I haven't been thinking about it anymore." The importance of control also became more salient as caregivers came to trust the eNeighbor technology: "You had asked if we wanted a monitor on the front door and I said never, but then the other day he actually tried to get out the door. It happened to be locked and he couldn't figure it out. I've never noticed that before. Now we want the monitor." Cumulatively, these preliminary studies suggest the potential and the feasibility of eNeighbor for ADRD caregivers.

2.3 Existing Literature:

The eNeighbor directly aligns with components of quality chronic disease care as proposed by healthcare experts and the Agency for Healthcare Research & Quality (AHRQ).³⁹⁻⁴² The eNeighbor and its integrated, remote sensor technology platform aims to prevent negative health transitions (i.e., falls, wandering) by allowing for a method of continuous monitoring and ongoing communication between the ADRD caregiver and a nurse care manager. The eNeighbor also allows for the appropriate management of chronic disease by episode instead of by health care professional encounter (e.g., regular visits to a primary care provider, emergency room visits), again resulting in a more proactive intervention approach. The remote monitoring platform of eNeighbor also allows chronic care to occur across locations as opposed to solely in formal medical settings. For these reasons, the eNeighbor intervention differentiates itself from many existing ADRD caregiver interventions which are often premised on crisis management (e.g., components of a psychosocial or clinical intervention are enacted only after a problem occurs, such as a wandering event or behavioral disruption).

This innovative dimension also becomes apparent when compared to other assistive devices, which do not provide person-centered, dynamic, time-sensitive information on older persons' functional behaviors. Specifically, eNeighbor uses complex algorithms that allow for the identification of routine function of the older adult and whether behaviors occur within or outside expected thresholds to trigger further health intervention. Current assistive devices such as bed alarms provide some degree of monitoring assistance, but are more oriented around crisis management rather than prevention (and existing evidence is not clear on the efficacy of these approaches). Similarly, while assistive supports such as hand rails may offer the least expensive solution, they are not able to provide real-time, monitoring data that is personalized to older persons at-risk. The potential of health monitoring technology such as eNeighbor is also increased due to the increasingly lowered costs associated with sensors and sensor maintenance. As the costs of these technologies decrease along with the concurrent increase in availability of cellular and broadband connectivity in U.S. households (see below), it is anticipated that health monitoring technology use will become more prevalent in caregiving households.

Health care experts have emphasized the need to better utilize technology to enhance care management, track patient outcomes, and effectively administer treatments.⁴³ While much is made of the promise of electronic health records or other technological advances, it remains

PROTOCOL TITLE: A Proactive Health Monitoring Intervention for Dementia Caregivers: The eNeighbor

fairly unknown whether they (or other technological aids)²⁴⁻³³ are actually effective for populations such as ADRD caregivers.⁴⁴⁻⁴⁷ A comprehensive review identified evidence demonstrating efficacy of health information technology in various chronic disease conditions to facilitate person-centered care as well as barriers to feasibility and utility, but no high quality studies existed demonstrating the efficacy of such technology for dementia family caregivers.⁴⁸ The proposed R18 demonstration will attempt to address this gap by examining the efficacy of health monitoring technology for persons with ADRD and their family caregivers to establish it as an evidence-based, innovative protocol.

A key component to this project is the integration of stakeholders' voices throughout the evaluation process. An active Community Advisory Board will serve in a collaborative capacity; it will engage with the PI on various research-related procedures, identify additional key open-ended questions to guide the process and outcome evaluation, explore barriers and facilitators to how health monitoring technology is delivered and utilized by persons with ADRD and their family caregivers, and assist in refining the evaluation design and dissemination to guide ongoing development along with the research team. Such engagement will be critical to ensuring that the benefits of health monitoring technology for persons with ADRD and their caregivers has high relevance for stakeholders.

The development and evaluation of the eNeighbor is grounded in a well-established conceptual model that has been used to successfully evaluate the efficacy of interventions for ADRD family caregivers.⁴⁹⁻⁵¹ The Stress Process Model (SPM) has been used extensively to study the manifestation of negative outcomes in dementia caregiving.⁵²⁻⁵⁵ The SPM is based on the mechanism of "proliferation," where the emotional stress of care provision to a person with dementia (primary stress) spreads to other life domains which are then posited to negatively influence global caregiving outcomes such as caregiver mental health or the person with ADRD's institutionalization. Psychosocial resources or formal service use may help stem stress proliferation and protect ADRD caregivers from negative outcomes.⁵³

The conceptual framework for the proposed project integrates constructs from the SPM. **Context of care** variables are conceptualized as key covariates; context of care considers key sociodemographic and background characteristics that may influence outcomes for persons with ADRD or their family caregivers. Similarly, **resource** variables such as perceptions of socioemotional support and community-based service use are considered as covariates in the eNeighbor conceptual model that could potentially alleviate negative outcomes. A final set of covariates considered in our conceptual model include **primary objective stressors**, or indices of dementia severity that may require greater day-to-day care provision on the part of family members. The proposed conceptual model positions eNeighbor as a key resource; the remote sensor technology of eNeighbor for dementia caregivers is hypothesized to independently and directly: **improve caregiver self-efficacy and competence, reduce caregiver distress** (subjective stress and depressive symptoms), **delay or reduce negative health transitions for the person with ADRD** (falls, wandering), and **delay or reduce the person with ADRD's service utilization** (residential care placement, hospitalization). The SPM is aligned with conceptualizations of

intervention effectiveness in the health information technology literature, suggesting that utilizing the SPM is appropriate when evaluating the efficacy of eNeighbor.⁵⁶

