analytic design of the study.⁶⁸ In this framework, the researcher identifies the Type I error rate (e.g., $p < .05$) to differentiate between a null and alternative test hypothesis, a suitable level of statistical power (.80 is considered an excellent power value), and the expected difference between the two study groups in order to determine the number of ADRD caregivers to enroll into the project. We sought a sample size that would be sufficient to detect a group difference of 0.50 standard deviation units. This is considered to be a “medium” effect size⁶⁹ and is a reasonable benchmark to evaluate the efficacy of a new behavioral intervention in comparison to an attention control condition. Using these specifications, a sample size of 200 ADRD caregivers (factoring in the anticipated 20% attrition rate) was found sufficient. As noted in various recommendations for mixed methods sampling, 30 participants is considered an adequate sample size for semi-structured interview protocols to ensure the richness and depth of open-ended data collected.^{70,71}

17.3 Statistical Analysis:

Analysis of Specific Aim1: Tests of Hypotheses 1-3.

Data available at baseline, 6 months, 12 months, and 18 months will allow for individual growth curve models that examine change in ADRD caregiver outcomes.^{72,73} Multilevel analysis approaches are available that support growth curve modeling. In this context, growth curve modeling is an example of a 2-stage modeling process consisting of 1) a within-subjects model across time; and 2) a between-subjects model that incorporates caregiver and person with ADRD covariates.^{74,75} The primary independent variable in the proposed investigation consists of an indicator variable for random assignment into the eNeighbor treatment condition or the attention care control. IBM SPSS Statistics 21⁷⁶ will be used to conduct these analyses, as it supports multilevel and growth curve modeling procedures. [name], the PI, has extensive experience conducting longitudinal and growth curve analyses in his prior research on ADRD caregiving.^{46,80,81,88}

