Our proposed analyses will provide in-depth tests of Hypotheses 1 and 2 and partially test Hypothesis 3 (i.e., rates of change in ADRD caregivers’ self-efficacy, competence, subjective stress, depressive symptoms, and frequency of negative health transitions and service use). In one set of outcome evaluations, the baseline value will be included as a covariate, and time will be “centered” at 6-months post-baseline. This scales the intercept effect to be a main effect of eNeighbor group assignment and allows the eNeighbor treatment and the attention control groups to have different 6-, 12-, and 18-month change trajectories, or an expanded eNeighbor treatment*time interaction effect. After establishing that the individual growth parameter estimates have significant variance around the mean trajectories of change in key dependent variables, an eNeighbor treatment vs. attention care control group indicator will be added as the key independent variable to predict intercepts and rates of change in outcomes. Additional analyses will determine if covariates (e.g., stress process model covariates including context of care indicators, primary objective stressors, and resources) significantly vary across the eNeighbor treatment and attention control groups at baseline and over time via growth curve modeling procedures. If statistically significant variations between the eNeighbor treatment and

PROTOCOL TITLE: A Proactive Health Monitoring Intervention for Dementia Caregivers: The eNeighbor

control groups are found, initial status and rate of change parameters for these covariates will be included in all tests to provide additional statistical control.

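### Section 17.3 admits prognostic covariates to the growth-curve tests only when the arms differ significantly, which gives up most of their precision and leaves near-significant imbalance uncorrected

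*Combined protocol and SAP*

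**What the plan says.** The conceptual framework in section 2.3 gives a prognostic reason for adjustment. Context-of-care "variables are conceptualized as key covariates; context of care considers key sociodemographic and background characteristics that may influence outcomes"; the same section also lists resources (such as socioemotional support) and primary objective stressors (dementia severity) as covariates.

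Section 17.3, tests of Hypotheses 1-3, sets the entry rule for the growth-curve models. "Additional analyses will determine if covariates (e.g., stress process model covariates including context of care indicators, primary objective stressors, and resources) significantly vary" between the arms, both at baseline and during follow-up. If statistically significant variations between the treatment and "control groups are found, initial status and rate of change parameters for these covariates will be included in all tests".

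Three other statements bear on this:
- Earlier in 17.3, the general description of the two-stage model says that its between-subjects part contains caregiver and care-recipient covariates. It names none and gives no rule.
- In one set of evaluations, 17.3 includes the outcome's own baseline value without any screen.
- The Cox models for Hypothesis 3, also in 17.3, take stress-process covariates with no significance condition.

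Section 5.3 adds that context-of-care items are collected at baseline only.

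**The concern.** A covariate earns its place in a randomised comparison by predicting the outcome. The screen in 17.3 asks a different question: whether the arms happen to differ on it. Arms come from a pre-generated random list (section 5.2), with no stratification described, so any baseline difference is due to chance. A strong predictor with an imbalance at p = .06 stays out, while an irrelevant variable at p = .04 goes in.

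Two things are at stake for the primary outcomes, caregiver self-efficacy and competence. One is precision that data already collected in both arms would supply. The other is protection in the single trial that will be run, should a prognostic variable be imbalanced just short of significance. The covariates in the primary model would also be settled by the data, and Aim 1 would treat the same covariates in two ways, screened in the growth-curve models and unscreened in the Cox models.

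**Working it through.** **Inputs from the documents.** Section 17.2 seeks to "detect a group difference of 0.50 standard deviation units" at p < .05 (two-sided assumed) with power .80, and states that "a sample size of 200 ADRD caregivers (factoring in the anticipated 20% attrition rate) was found sufficient". Section 1.0 has 100 persons with ADRD and their caregivers "randomly assigned to an eNeighbor treatment condition when compared to 100 usual care controls". So 100 per arm are randomised, and 80 per arm are analysed after 20% attrition.

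**Assumptions.** The documents give no covariate-outcome correlation. Let r be the correlation of one further baseline covariate with the outcome variation left after the baseline outcome is adjusted for, with r from 0.1 to 0.5. That remaining variation is given SD 1, and a two-group comparison stands in for the growth-curve contrast.

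**The plan's own figure.** n per arm = 2(1.96 + 0.84)²/0.50² = 63 (rounded up), so 126 in total, and 126/0.80 = 158. The stated 200 is not reproduced, but it exceeds 158. The plan used a multilevel method whose variance inputs are not given, so 200 is not an error and nothing below depends on it. With 80 per arm, 0.50/√(2/80) = 3.16, and simple power is Φ(3.16 − 1.96) = .885.

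**Entry rate.** Each baseline test has a true null, so entry is about 5% per covariate. If 5 or 10 independent covariates were screened (the number is not stated), the chance that at least one enters by luck is 1 − .95⁵ = 23% or 1 − .95¹⁰ = 40%.

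**Precision.** Adjustment multiplies the standard error by √(1 − r²), so power at 0.50 SD is Φ(3.16/√(1 − r²) − 1.96).

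**Imbalance that passes the screen.** With 100 per arm, differences up to 1.96 × √(2/100) = 0.277 SD are not significant. The resulting shift in the estimate is r × 0.277.

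**Conditional error.** Given covariate imbalance z, the unadjusted test statistic under the null is N(rz, 1 − r²). At z = 1.9 (p about .06, so excluded) the error is P(|N(1.9r, 1 − r²)| > 1.96).

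**Overall error.** Averaging that error over |z| < 1.96, and adding .05 × .05 for trials where the covariate enters, gives the last column.

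| r | Power at 0.50 SD, always adjusted | Shift at 0.277 SD imbalance | Error at z = 1.9 | Overall error under the rule |
|---|---|---|---|---|
| 0.1 | .89 | 0.03 SD | .053 | .050 |
| 0.2 | .90 | 0.06 SD | .062 | .049 |
| 0.3 | .91 | 0.08 SD | .077 | .048 |
| 0.4 | .93 | 0.11 SD | .097 | .046 |
| 0.5 | .955 | 0.14 SD | .122 | .043 |

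The shifts are about 6% to 28% of the 0.50 SD target (0.028/0.50 to 0.139/0.50).

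**Simulation of the baseline screen** (80 per arm, 20,000 trials per setting):

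| True effect | r | Unadjusted | Screen | Always adjusted |
|---|---|---|---|---|
| 0.40 SD | 0.3 | .710 | .713 | .750 |
| 0.40 SD | 0.5 | .706 | .716 | .821 |
| 0.50 SD | 0.3 | .884 | .886 | .911 |
| 0.50 SD | 0.5 | .882 | .890 | .949 |

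The screen stays close to the unadjusted analysis. With no true effect, its overall error was .050 (r = 0.3) and .045 (r = 0.5), and the mean estimate was about zero. In trials with covariate p between .05 and .15 in one direction, it left a bias of about 0.08 SD (r = 0.3) or 0.13 to 0.14 SD (r = 0.5). Always adjusting left about 0 to 0.01.

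**The case against.** **Overall validity is intact.** This stands in full. A reader might infer that the screen inflates the trial's false-positive rate or biases the treatment effect. Neither follows. The raised error near z = 1.9 is offset by an error below nominal when the covariate is balanced (at z = 0: .040, .032 and .024 for r = 0.3, 0.4 and 0.5).

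**Power is already adequate.** This largely stands at the planned effect. Simple power of about .885 exceeds the .80 target without further covariates, and at r = 0.1 the gain is negligible. If the 0.50 SD refers to raw outcome units, adjusting for the baseline outcome lifts the starting power and narrows the gain further. The gain is larger for smaller true effects.

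**The general model description already contains covariates.** Section 17.3 could be read as a covariate model with an extra screen on top. But no base set is named apart from the outcome's baseline value, so the screen is the only working rule for the stress-process covariates. On either reading a list is needed.

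**The written screen is wider than a baseline test.** This stands as a limit. The screen also looks at differences over time, where randomisation guarantees no null for measures repeated after assignment. The 5% and 23-40% entry figures therefore describe only the baseline part, which is the only part open to context-of-care items. Adjusting for post-randomisation change is a separate question, not settled here.

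**Conclusion.** The concern holds as a matter of efficiency and pre-specification. The entry rule in 17.3 does not serve the purpose given in section 2.3, which says only that the variables may influence outcomes, and it differs from the handling in the Cox models.

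The cost has two parts. Power forgone at 0.50 SD runs from almost nothing at r = 0.1 to about six or seven points at r = 0.5. In trials where a prognostic covariate is imbalanced just short of significance, the estimate may shift by about 0.03 to 0.14 SD and the conditional error is about .05 to .12.

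These sizes rest on an assumed range of correlations, one covariate, 80 analysed per arm and a simple two-group approximation. The documents do not support saying that the trial is underpowered, or that its overall error rate exceeds 5%. The change is worth making because it is cheap and removes a data-dependent choice from the primary tests.

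**What to change.** In section 17.3, delete the significance screen for baseline covariates. State that every growth-curve model for Hypotheses 1-3 includes, whatever the observed imbalance:
- the baseline value of the outcome;
- the baseline dementia-severity (primary objective stressor) index and baseline socioemotional support, both drawn from the section 2.3 framework;
- a few context-of-care characteristics that the sponsor fixes before any unblinded analysis. Kin relationship and caregiver gender are candidates. Section 2.3 does not name them, but section 5.3 already uses them as sampling strata for the post-evaluation interviews.

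Report baseline differences descriptively, without p-values. Align the general model description in 17.3 with this list.

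The cost is plan wording and four or five degrees of freedom out of about 160. No new data are needed if the chosen items are already in the baseline survey, which both arms complete.
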